7.3 Mechanistic objectives

Mechanistic objectives of this study are to determine if OM85 modulates:

- Seroconversion to COV
- Host immune cell profile grouped who test respectively positive or negative to COV during an ARI, including LRI, and stratified by treatment (COV⁺/OM⁺, COV⁺/OM⁻, COV⁻/OM⁺, COV⁻/OM⁻).
- White blood cell transcriptomic profile by group (COV⁺/OM⁺, COV⁺/OM⁻, COV⁻/OM⁺, COV⁻/OM⁻).
- White blood cell cytokine production profile by group (COV⁺/OM⁺, COV⁺/OM⁻, COV⁻/OM⁺, COV⁻/OM⁻).

7.4 Safety objectives

The safety objective of this study is to determine if administration of OM85 is safe when treating front line HCW.

8. Study Design

8.1 Description

This study will be conducted as a multi-centre, parallel group, wait list design clinical trial testing the reduction of acute severe respiratory events requiring workforce removal in HCW with OM85. Health Care Workers who are eligible will receive daily OM85 for 3 months. Group 1 “Wait-list group” will be given daily OM85 for 3 months commencing in Month 3, with 3 months follow-up off treatment. Group 2 “Initial treatment group” will be given daily OM85 for 3 months commencing in on day 0, with 3 months follow-up off treatment

8.2 Efficacy Endpoints

8.2.1 Primary efficacy endpoint

The primary endpoint is the proportion of HCW contracting an ARI necessitating workforce removal

8.2.2 Secondary efficacy endpoints

Secondary endpoints include:

- The time to ARI necessitating workforce removal
- The proportion of HCW contracting an ARI necessitating workforce removal at end of treatment and at the end of the follow-up period, overall and by department
- The total number of days with respiratory symptoms (upper or lower)
- The proportion of HCW with COV infection documented by PCR, seroconversion and/or COV ARI necessitating workforce removal.
- The time to LRI necessitating workforce removal
- The proportion of HCW contracting an LRI necessitating workforce removal at end of treatment and at the end of the follow-up period, overall and by department
- The proportion of HCW with COV infection documented by PCR, seroconversion and/or COV LRI necessitating workforce removal.

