10.1.7 Patient daily symptom data

Following randomisation, the process will be explained to participants concerning their documentation of /response to daily SMS regarding any respiratory symptoms. These symptoms and/or condition related to the symptoms will be recorded as adverse events. Unclear or missing entries will be clarified with the participant and any correction annotated by site staff as appropriate. Annotations made by site staff will be clearly identified and initialled and dated.

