10.1.8 Telephone calls

Telephone calls may be conducted during the study to ensure patient compliance with investigational product and completion of daily symptom data. If required, telephone calls will be conducted to assess adverse event data and review of concomitant medications and therapies will be undertaken. These may be conducted via SMS or email if participant prefers.

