10.2 Scheduled visits

This study consists of 5 visits (Group 1 - WLC) or 4 visits (Group 2 – initial treatment) over 6 or 9 months respectively (see Figure 1) Study procedures to be performed at each visit are detailed in the Schedule of Assessments and Procedures in Appendix 1.

Visits should be conducted within the specified visit windows where possible.

Figure 1: Study timeline and procedures. Nasal swab collection (blue arrow), blood collection (red arrow).

Group 1 (WLC)

Visit 1 – Screening and randomisation

The following assessments and procedures will be performed and recorded at this visit:

- Obtain written informed consent
- Evaluate inclusion and exclusion criteria
- Obtain demographic history
- Obtain medical history
- Vital signs
- Explain daily respiratory symptom data collection and assist with collection for Day 0

Once all screening procedures have been completed and eligibility confirmed, the participant will be registered with the Sponsor. Further information on the registration process is provided in the Study Reference Manual.

Visit 2: Treatment initiation 3 months post randomisation (±5 days)

- Update demographic & medical history
- Vital signs

- Nasal swab
- Collection of blood samples
- Dispense study medication and explain administration
- Adverse event assessment

Visit 3: Treatment cessation 6 months post randomisation (± 5 days)

- Vital signs
- Nasal swab
- Collection of blood samples
- Clarify any missing data (daily respiratory symptoms) with participant, if not previously addressed by email/SMS
- Adverse event assessment
- Collect used investigational product packaging and unused investigational product

Visit 4: Follow up cessation 9 months post randomisation (± 5 days)

- Vital signs
- Nasal swab
- Collection of blood samples
- Clarify any missing data (daily respiratory symptoms) with participant, if not previously addressed by email/SMS
- Adverse event assessment

Unscheduled Visit: at time of ARI necessitating workforce removal

- Vital signs
- Nasal swab
- Collection of blood samples
- Clarify any missing data (daily respiratory symptoms) with participant, if not previously addressed by email/SMS
- Adverse event assessment

Group 2 (Initial Treatment)

Visit 1 – Screening, randomisation, and treatment initiation

The following assessments and procedures will be performed and recorded at this visit:

- Obtain written informed consent
- Evaluate inclusion and exclusion criteria
- Obtain demographic history

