- Obtain medical history
- Vital signs
- Nasal swab
- Collection of blood samples
- Drug delivery
- Dispense study medication and explain administration
- Explain daily respiratory symptom data collection and assist with collection for Day 0

- Adverse event assessment

Once all screening procedures have been completed and eligibility confirmed, the participant will be registered with the Sponsor. Further information on the registration process is provided in the Study Reference Manual.

Visit 2: Treatment cessation 3 months post randomisation (± 5 days)

- Vital signs
- Nasal swab
- Collection of blood samples
- Clarify any missing data (daily respiratory symptoms) with participant, if not previously addressed by email/SMS
- Adverse event assessment
- Collect used investigational product packaging and unused investigational product

Visit 3: Follow up cessation 6 months post randomisation (± 5 days)

- Vital signs
- Nasal swab
- Collection of blood samples
- Clarify any missing data (daily respiratory symptoms) with participant, if not previously addressed by email/SMS
- Adverse event assessment

Unscheduled Visit: at time of ARI necessitating workforce removal

- Vital signs
- Nasal swab
- Collection of blood samples
- Clarify any missing data (daily respiratory symptoms) with participant, if not previously addressed by email/SMS
- Adverse event assessment

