13.2.2 Statistical analyses

The *interim analysis*, undertaken at month 1 on both the "intention-to-treat" and "per protocol" groups, will examine the primary outcome: if the treatment difference is statistically significant in favour of OM85 the DSMB will consider immediately switching WLC participants to OM85.

Between-group differences in the primary outcome at 3 months will be assessed using log-binomial regression. Secondary outcomes measured to follow-up cessation will be assessed using mixed-effects models with group and stage (treatment/follow-up) (main effects and interaction) as fixed effects and HCW as random effect. Time-to-ARI analyses will use the log-rank test. Analyses will be undertaken on both the "intention-to-treat" and "per protocol" groups.

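### Total symptom days is analysed with no stated window and no term for days observed, so any unequal diary capture that remains between groups would bias the comparison

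*Combined protocol and SAP*

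**What the plan says.** The endpoint in section 8.2.2 is "The total number of days with respiratory symptoms (upper or lower", with no time window or denominator. Section 10.1.7 gives the source as participants' "documentation of /response to daily SMS regarding any respiratory symptoms".

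Three provisions deal with gaps in the diary:
- Section 10.1.7: "Unclear or missing entries will be clarified with the participant and any correction annotated by site staff as appropriate". No time limit is set.
- Section 10.1.8: "Telephone calls may be conducted during the study to ensure patient compliance with investigational product and completion of daily symptom data". This contact is optional and may be by SMS or email.
- Section 10.2, at certain visits: "Clarify any missing data (daily respiratory symptoms) with participant, if not previously addressed by email/SMS". The step is listed for Group 1 Visits 3 and 4, Group 2 Visits 2 and 3, and unscheduled visits. It is not listed for Group 1 Visit 2. Appendix 1 marks diary review at that visit.

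On analysis, section 13.2.2 states: "Secondary outcomes measured to follow-up cessation will be assessed using mixed-effects models". The fixed effects are group, stage (treatment or follow-up) and their interaction, and the worker is the random effect. Section 13.3.2 repeats this. Neither section names an offset, a days-observed term, a distribution or a link. No rule says how an unanswered day, or a day after withdrawal, enters the total.

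**The concern.** A total depends on how many days were observed as well as on how many had symptoms. With no denominator and no missing-day rule, a day nobody recovers contributes zero, just as a symptom-free day does. Diary effort could differ between workers who hold the drug and workers still waiting for it, because no placebo is described. Any such difference would pass into the treatment estimate, in either direction.

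The text also contains a specific route to unequal capture. At month 3, the end of the only period with an untreated control, the visit lists prompt staff to recover missing diary days in Group 2 but not in Group 1.

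**Working it through.** **The plan's own figures.** None is given for this endpoint. The power statements in section 13.2 concern the primary endpoint. For 500 per group and 20% versus 13.5%, the stated 80% comes out at 78.7% (two-sided 0.05, pooled normal approximation). It has no bearing on symptom days.

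**Month 3, side by side.** Group 1: "Visit 2: Treatment initiation 3 months post randomisation (±5 days"; no diary clarification in the section 10.2 list. Group 2 Visit 2, same time point; clarification listed. Appendix 1: diary review marked for both.

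**Planned observation from randomisation.** Group 1 runs to day 270. Group 2 ends at "Visit 3: Follow up cessation 6 months post randomisation (± 5 days", about 180 days, but Appendix 1 gives Day 120. The ratios are 270/180 = 1.5 and 270/120 = 2.25. A total taken from randomisation to follow-up cessation would therefore differ by group even with perfect diaries and no drug effect.

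**Effect of unequal capture.** All inputs here are assumptions, because the documents give no mean, spread or completion rate: true mean 6 symptom days in both arms, negative binomial with dispersion k, fraction c of symptom days captured, and the remainder never recovered.

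- Captured mean m = 6c; variance m + m²/k.
- z = (m₁ − m₂) / √[(v₁ + v₂)/n]; rejection rate = Φ(z − 1.96) + Φ(−z − 1.96).

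For 90% versus 80%, k = 0.5, n = 1000 per arm: m = 5.4 and 4.8; v = 5.4 + 58.32 = 63.72 and 4.8 + 46.08 = 50.88; SE = √(114.60/1000) = 0.3385; z = 0.6/0.3385 = 1.77; rejection rate 42.6%.

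For k = 0.3: v = 102.6 and 81.6; SE = √(184.2/1000) = 0.4292; z = 1.40; rejection rate 28.7%.

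| Capture | k = 0.5, 1000/arm | k = 0.3, 1000/arm | k = 0.5, 500/arm | k = 0.3, 500/arm |
|---|---|---|---|---|
| 90% v 85% | 13.9% | 10.4% | 9.4% | 7.7% |
| 90% v 80% | 42.6% | 28.7% | 24.1% | 16.7% |
| 90% v 75% | 77.9% | 57.7% | 48.8% | 33.1% |

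The nominal rate is 5%.

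**Cross-check by simulation.** Null gamma-Poisson counts over 90 days, mean 5 or 9, shape 0.5 or 1, 2000 runs per scenario, missing days unrelated to symptoms. At 90% versus 80%, raw totals reject in 23% to 42% of runs with 500 per group and 42% to 70% with 1000. The spurious difference is the mean times the gap: 5 × 0.10 = 0.5 day to 9 × 0.10 = 0.9 day. Dividing by the completion fraction brings rejection back to 4% to 6% in every scenario.

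**Limit of an offset.** Take 90 days with 6 symptom days and 84 symptom-free days in both arms.
- Symptom days captured 90% versus 80%, symptom-free days 90% in both: days answered are 5.4 + 75.6 = 81.0 and 4.8 + 75.6 = 80.4. The raw ratio is 4.8/5.4 = 0.889; the offset ratio is (4.8/80.4)/(5.4/81.0) = 0.896. Almost nothing is corrected.
- All symptom days captured, symptom-free days 90% versus 70%: days answered are 6 + 75.6 = 81.6 and 6 + 58.8 = 64.8. The raw ratio is 1.00; the offset ratio is (6/64.8)/(6/81.6) = 1.26. The offset introduces a bias that the raw total does not have.

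**The case against.** A reader might infer that unequal diary completion is by itself enough to create a treatment difference. The documents do not support that. They never say blank days are scored as symptom-free, and they provide for recovering them. If every missing day is recovered accurately, the bias calculated above is zero. If days are recovered inaccurately, the problem becomes differential recall, which the calculation does not model and an offset would not cure.

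A reader might also infer that gaps are routinely filled by three-month recall with unblinded staff. Visit clarification applies only where email or SMS has not already settled the matter. Nor do the documents say who clarifies entries or whether that person knows the allocation. Knowledge of allocation is a fair inference from a wait-list design with no placebo described, and from a section 13.1 that has blinding in its heading and describes none, but it is still an inference.

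Nor should the silence on distribution be read as choosing a normal model. The same phrase covers secondary outcomes that are proportions, so it can include a generalised model for counts. The fault is under-specification. Likewise, if totals were formed within stage, the text gives 90 days per stage in both groups. Appendix 1 would still leave Group 2 with 120 − 90 = 30 follow-up days against 270 − 180 = 90 in Group 1, and the two-level stage factor has no level for Group 1's untreated months 0–3.

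Finally, the false-positive rates rest on assumed inputs and a test of means rather than the planned model. They show that a gap would matter, not that one is likely. All of this stands, and it makes the point conditional. It does not supply the missing window, missing-day rule or days-observed term.

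**Conclusion.** The concern holds in conditional form. The endpoint is an unadjusted count, nothing in the stated model accounts for days observed, and the month-3 visit lists treat the groups differently, in conflict with Appendix 1. If a 10-point capture gap remained after clarification, the false-positive rate would be about 29% to 43% with 1000 per arm, or about 17% to 24% with 500, given a mean of 6 days, dispersion 0.3 to 0.5 and no drug effect. Separately, and without any assumption about diary behaviour, planned follow-up from randomisation is 270 days against 180 or 120.

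This is a change that should be made, not one on which the trial depends: it concerns one secondary endpoint and leaves the primary analysis untouched.

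**What to change.** 1. Define the window: use months 0–3 for the randomised comparison of symptom days.
2. Analyse with a negative binomial or other count model, with log of diary days observed in that window as offset. State how unanswered and post-withdrawal days are handled.
3. Reconcile the section 10.2 Group 1 Visit 2 list with Appendix 1, so that both groups have the same diary clarification at month 3. Reconcile the two timings given for Group 2's last visit.
4. Date-stamp recovered entries and report diary completion by group.
5. Add sensitivity analyses that exclude late-recalled entries and that allow missingness to depend on symptoms. Excluding recovered entries from the main result would be debatable, since it discards the protocol's only means of repairing gaps.

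The cost is analysis-plan wording, one procedural line and one date field. The downside is that the offset assumes answered days represent unanswered ones. When missingness depends on symptoms it may correct little (0.896 against 0.889 above) or add bias (1.26 against 1.00), so items 4 and 5 are needed alongside it.

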Primary endpoint	The proportion of HCW contracting an ARI necessitating workforce removal.
Secondary endpoints	
Secondary endpoints include:
 
 • The time to ARI necessitating workforce removal • The proportion of HCW contracting an ARI necessitating workforce removal at end of treatment and at the end of the follow-up period, overall and by department • The total number of days with respiratory symptoms (upper or lower) • The proportion of HCW with COV infection documented by PCR, seroconversion and/or COV ARI necessitating workforce removal. • The time to LRI necessitating workforce removal • The proportion of HCW contracting an LRI necessitating workforce removal at end of treatment and at the end of the follow-up period, overall and by department • The proportion of HCW with COV infection documented by PCR, seroconversion and/or COV LRI necessitating workforce removal.
Mechanistic endpoints	
Mechanistic endpoints (Brisbane only) include:
 
 • Seroconversion to COV • Host immune cell profile grouped who test respectively positive or negative to COV during a ARI and stratified by treatment (COV⁺/OM⁺, COV⁺/OM⁻, COV⁻/OM⁺, COV⁻/OM⁻).

- White blood cell transcriptomic profile by group (COV⁺/OM⁺, COV⁺/OM⁻, COV⁻/OM⁺, COV⁻/OM⁻).
- White blood cell cytokine production profile by group (COV⁺/OM⁺, COV⁺/OM⁻, COV⁻/OM⁺, COV⁻/OM⁻).

Safety endpoints	
Safety endpoints include:
 
 • Treatment-related adverse events • Routine haematology and clinical chemistry
Inclusion criteria	
Participants who meet all of the following criteria are eligible for enrolment:
 
 1. HCW “front line” clinical departments assessing or caring for patients with suspected or proven COV infection at one of the recruiting hospitals in Brisbane or London 2. Participants who, in the opinion of the investigator, are able to comply with the protocol for its duration 3. Written informed consent signed and dated by participant according to local regulations
Exclusion criteria	
Participants who meet any of these criteria are not eligible for enrolment:
 
 1. Staff with prior COV infection necessitating workforce removal.
Treatment description	Broncho-Vaxom adult capsules® (OM85)

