8.2.3 Mechanistic endpoints

- Seroconversion to COV
- Host immune cell profile grouped who test respectively positive or negative to COV during an ARI, including LRI, and stratified by treatment (COV⁺/OM⁺, COV⁺/OM⁻, COV⁻/OM⁺, COV⁻/OM⁻).
- White blood cell transcriptomic profile by group (COV⁺/OM⁺, COV⁺/OM⁻, COV⁻/OM⁺, COV⁻/OM⁻).
- White blood cell cytokine production profile by group (COV⁺/OM⁺, COV⁺/OM⁻, COV⁻/OM⁺, COV⁻/OM⁻).

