9.3 Criteria and procedures for participant withdrawal

9.3.1 Withdrawal of participants from study

Participants will be withdrawn from the study if any of the following conditions are met:

- The participant withdraws their consent
- The participant fails to return to the clinic (i.e., they are lost to follow-up or death)
- The site investigator or his/her designee believes that continuation in the study is no longer in the participant's best interests (which may be as a result of the occurrence of adverse events (AE) or clinically relevant laboratory results)
- The participant is unable to comply with the protocol, including completing required study treatments, procedures, tests and/or examinations
- The Sponsor reserve the right to terminate the entire study or any participants involvement at any time

Participants who prematurely discontinue investigational product will be encouraged to continue with the study visit schedule and assessments. For further information regarding Early Withdraw Visits refer to Section 10.4.

Those participants that cease the investigational product before the end of the study, but continue to be assessed for all other aspects of the study, will be regarded as members of the intention to treat (ITT) sample. All remaining study medication (including used and unused medication and packaging) will be collected.

In all cases, the reason and date of withdrawal from the study, or investigational product, will be completed in the source documentation and the CRF. If the withdrawal is due to an adverse event or a clinically significant laboratory result, the participant will be followed until the AE is resolved or is clinically stabilised. The AE or laboratory result must be recorded in the CRF.

If a participant tests positive to a clinical test (not part of the study) they will follow the hospital isolation protocol. The study Covid testing is done by measuring antibodies, which are not suitable for acute surveillance as it detects past infection. Results (positive or negative) will be returned to participant for their own information

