10.1.6 Blood tests

Venous blood samples will be collected at four time points (shown in Figure 1) for viral serology and immune profiling.

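### COV seroconversion in months 0-3 cannot be ascertained alike in the two arms, because Group 1 has no scheduled blood or swab before day 90 and no counting rule is given.

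*Combined protocol and SAP*

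**What the plan says.** Section 8.2.2 lists two COV composites as secondary endpoints: "The proportion of HCW with COV infection documented by PCR, seroconversion and/or COV ARI necessitating workforce removal" and "The proportion of HCW with COV infection documented by PCR, seroconversion and/or COV LRI necessitating workforce removal". Section 8.2.3 adds "Seroconversion to COV" as a mechanistic endpoint. The Synopsis limits that family to one country: "Mechanistic endpoints (Brisbane only) include".

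Under Section 8.1, Group 1 "will be given daily OM85 for 3 months commencing in Month 3". Months 0-3 are therefore the only period with an untreated control. Section 13.3.1 ties the primary analysis to that period.

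Section 10.2 lists no blood and no swab for Group 1 at Visit 1. They first appear under "Visit 2: Treatment initiation 3 months post randomisation". Group 2 has both at Visit 1. Appendix 1 shows the same pattern: bloods and swabs start at day 90 in Group 1 and at day 0 in Group 2. Section 10.1.6 states: "Venous blood samples will be collected at four time points (shown in Figure 1) for viral serology and immune profiling".

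Section 9.2 excludes earlier COV infection only where it took the person off work. Section 9.3.1 says of the assay: "The study Covid testing is done by measuring antibodies, which are not suitable for acute surveillance as it detects past infection".

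Sections 13.2.2 and 13.3.2 send the secondary and mechanistic endpoints to a mixed model with group and stage, the stages being treatment and follow-up. Section 13.3 schedules endpoint analyses at 3 months without naming the endpoints.

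**The concern.** Seroconversion means a negative sample followed by a positive one. Over months 0-3 Group 2 has the pair and Group 1 has only the second sample. People with mild or unrecognised earlier infection can enroll, so a positive Group 1 result at day 90 mixes infection before and after randomisation. The exception is anyone who had an unscheduled blood earlier, and that requires a respiratory infection that took them off work.

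The PCR component has a similar asymmetry, because only Group 2 is swabbed at day 0. Counting positives on that swab as events would work against OM85.

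At stake is a fair untreated comparison for the seroconversion part of two secondary endpoints and for one mechanistic endpoint. If the arms are counted differently, a difference can appear with no drug effect.

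**Working it through.** **Sampling in months 0-3** (Section 10.2 and Appendix 1)

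| | Day 0 | Before day 90 | Day 90 |
|---|---|---|---|
| Group 1 (wait list) | none | unscheduled visit only | blood, swab |
| Group 2 (initial treatment) | blood, swab | unscheduled visit only | blood, swab |

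Figure 1 is not available, but the visit lists and Appendix 1 agree. The four time points fit both arms as three scheduled samples plus one unscheduled, so they do not imply a day-0 sample in Group 1.

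**The plan's own figures** (Section 13.2, which concern ARI). Pooled two-proportion z-test, two-sided 0.05 (sidedness is not stated in the plan):
- 20% vs 13.5%, 500 per arm: power 78.7% (stated 80%).
- 20% vs 15%, 1000 per arm: power 83.8% (stated 80%).

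**Illustration of unequal counting, serology component only.** Assumptions: no drug effect; 3-month incidence i = 0.20, borrowed from Section 13.2; perfect assay; baseline seroprevalence s of 1% to 10% (the documents give none); Group 1 day-90 positives counted as conversions.
- Group 1 counted positive: s + (1-s)i.
- Group 2 conversions among all randomised: (1-s)i.
- Alternative for Group 2: rate i among the (1-s)n who were negative at baseline.

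Example, s = 0.05: Group 1 is 0.05 + 0.95 × 0.20 = 0.240; Group 2 is 0.95 × 0.20 = 0.190; RR = 0.190/0.240 = 0.79. With the at-risk denominator, RR = 0.20/0.240 = 0.83.

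The last two columns give the chance of a significant result in favour of OM85 (nominal 2.5%). Each cell shows the all-randomised denominator first and the at-risk denominator second.

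| s | Apparent RR | 1000 per arm | 500 per arm |
|---|---|---|---|
| 1% | 0.95 / 0.96 | 8.0% / 6.5% | 5.9% / 5.0% |
| 2% | 0.91 / 0.93 | 19.6% / 13.9% | 11.9% / 9.0% |
| 5% | 0.79 / 0.83 | 77.7% / 56.8% | 48.6% / 32.4% |
| 10% | 0.64 / 0.71 | >99.9% / 98.3% | 96.5% / 82.2% |

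The 500-per-arm column is the one for the Brisbane-only mechanistic endpoint.

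**Counting alike: day-90 seropositivity in both arms.** With incidences i1 and i2, p1 = s + (1-s)i1 and p2 = s + (1-s)i2.
- Risk difference: p1 - p2 = (1-s)(i1 - i2), which is the difference in incident infection among all randomised. At s = 0.05 with 20% vs 15%: 0.2400 - 0.1925 = 0.0475 = 0.95 × 0.05.
- With no effect, RR = 1 at every s.
- A true RR of 0.75 reads 0.76, 0.77, 0.80 or 0.84 at s = 1%, 2%, 5% or 10%. Subtracting s restores it: (0.1925 - 0.05)/(0.2400 - 0.05) = 0.1425/0.19 = 0.75.
- Power, 20% vs 15%, 1000 per arm: 83.8% falls to 81.7%, 79.6%, 73.3% or 63.4%.
- Power, 20% vs 13.5%, 500 per arm: 78.7% falls to 76.3%, 73.9%, 67.1% or 56.9%.

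**The case against.** A reader might infer that OM85's effect on COV infection against no treatment cannot be learned from these samples. That goes too far. Randomisation balances baseline seroprevalence in expectation, so the day-90 difference recovers the incident difference, as shown above. What is unavailable is individual seroconversion in Group 1.

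A reader might also take the table as the bias of the planned analysis. The documents do not support that either. No section says that undated Group 1 positives count as conversions, and doing so would strain the ordinary meaning of the word. If documented conversion were required and Group 1 members without a baseline were counted as non-events, the bias would reverse. The table also leaves out PCR, so it does not model the whole composite.

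Nor can it be said that the mixed model omits the untreated months. Stage is undefined for Group 1's waiting period. If it means trial period, the first stage includes untreated controls; if it means time relative to treatment start, they belong to neither stage.

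Finally, sampling aligned to the start of treatment is a coherent design, and by the visit text it is matched on that scale. (Appendix 1 puts Group 2's last scheduled visit at day 120 and Section 10.2 at 6 months; these need reconciling.) Alignment on that scale still gives no matched samples for the untreated comparison. These objections narrow the point, but the unequal sampling and the missing rule stand.

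**Conclusion.** The concern holds in a limited form. Over the only untreated-control period, the seroconversion part of the two COV secondary endpoints, and the mechanistic seroconversion endpoint, cannot be ascertained alike in the two arms. Group 2's day-0 swab creates a similar asymmetry for PCR. The plan does not say how Group 1's day-90 positives are counted or where its untreated months sit in the model.

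No direction or size of bias is established, because both depend on the unstated rule and the unstated seroprevalence. Under the one rule illustrated, the problem is not negligible even at 1% seroprevalence: about 6% to 8% false significance favouring OM85 at 1000 per arm, against a nominal 2.5%. The primary endpoint is untouched. The sponsor should settle this before data are seen, but it does not threaten the trial's main conclusion.

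That the effect is recoverable from day-90 serology rests on randomisation, a perfect assay, antibodies persisting to day 90, and day-90 samples being obtained alike in both arms.

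**What to change.** For the between-arm comparison over months 0-3:
- Define COV infection only from samples taken alike in both arms: day-90 serology, day-90 swab and unscheduled-visit samples. Count no events from Group 2's day-0 samples.
- Label the serology part as day-90 seropositivity, not seroconversion.
- Report the risk difference. As a sensitivity analysis, use Group 2's day-0 seroprevalence to estimate s and correct the diluted risk ratio.
- State which comparison the COV endpoints use, and to which stage Group 1's months 0-3 belong.

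This needs no added sample, but it is more than a change of label: part of two secondary endpoints and a mechanistic endpoint become prevalence at day 90. The price is the power loss shown in the working, for example from 83.8% to 73.3% at 5% seroprevalence with 1000 per arm. If seroconversion itself must be compared with untreated controls, a day-0 blood at Group 1's existing Visit 1 would supply it, at about 500 extra samples for Brisbane or 1000 for both countries.
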